1 PROTOCOL SUMMARY

1.1 SYNOPSIS

Title:

Safety and efficacy of non-invasive Vagus Nerve Stimulation (nVNS) in the treatment of headache in Subarachnoid Hemorrhage (SAH)

Study Description: This is a single site, randomized, sham-controlled, double-blind study assessing the feasibility, safety, tolerability, and efficacy of non-invasive VNS (nVNS) in the treatment of headache in subarachnoid hemorrhage (SAH). We hypothesize that two-two minute noninvasive stimulations of the cervical branch of the Vagus nerve, every 5 hours, is efficacious in safely reducing headache intensity and frequency in patients with headache due to SAH, during the patient's intensive care unit (ICU) stay. After screening and obtaining informed consent, eligible patients diagnosed with SAH on head scans, admitted to the Neurosurgical Intensive Care Unit (NSCU) at Northshore University Hospital will be randomized to either the treatment (stimulation of the cervical branch of the Vagus nerve) or sham (inactive stimulation) group. Pain intensity will be evaluated every 4 hours. Non-invasive stimulation will be performed

	every 5 hours. Device related adverse events, mean headache intensity, and mean and peak morphine equivalence dosage during the study period will be compared between the VNS group and the sham group. Patients will be on continuous telemetry with frequent vital sign measurement. Opiate related adverse events will also be monitored.
Locations	North Shore University Hospital Lenox Hill Hospital Yale University Hospital- for specimen processing
Objectives:	
	The primary objective of this study is to examine the safety and efficacy of nVNS as a treatment for headache in subarachnoid hemorrhage (SAH).
Endpoints:	The primary safety endpoint for this study is the incidence of device related serious adverse events.
	The primary outcome measurements for effectiveness is:
	-The difference between the active and sham treatment groups in morphine equivalence dosage
	Secondary endpoints include descriptive comparisons between the active and sham treatment groups in:
	 The difference between the active and sham treatment groups in the mean daily headache intensity
	 The difference between total overall morphine equivalence dosage between the active and sham group per subject during study
	-Opiate related adverse events (such as urinary retention, constipation, sedation, respiratory depression, nausea, vomiting and pruritis)

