3 OBJECTIVES AND ENDPOINTS

The primary outcome measurement for effectiveness is:

-The difference between the active and sham treatment groups in mean daily morphine equivalence dosage during study

Secondary endpoints include descriptive comparisons between the active and sham treatment groups in:

- The difference in mean daily headache intensity during the study

The difference between total overall morphine equivalence dosages per subject during study
 Opiate related adverse events (such as urinary retention, constipation, sedation, nausea, vomiting and pruritis)

- The difference in cytokines levels and brain permeability markers in the blood and/or CSF before and after stimulation and between the sham and active device group

- Effects of VNS on brain permeability measured through CT perfusion studies

-The difference in modified rankin scale at hospital discharge and during outpatient follow up. This will be collected retrospectively from the follow up outpatient visit.

Exploratory analyses will include descriptive comparisons of the rates of stroke, vasospasm, DCI, seizure, central fever and severity of vasospasm between the active and sham treatment groups.

OBJECTIVES	ENDPOINTS
Primary Objective:	

Incidence of device related serious adverse events.	Proportion of patients with device related adverse events
The difference between the active and sham treatment groups in mean daily morphine equivalence dosage during study	Morphine equivalence dosage will be calculated per day.
Secondary Objectives	
The difference between the active and sham treatment groups in the mean daily headache intensity during the study	Headache intensity will be measured throughout the day and a mean daily headache intensity will be calculated.
The difference between total overall morphine equivalence dosage between the active and sham group per subject during study	Total morphine equivalence dosage for the duration of the study will be calculated.
Incidence of opiate related adverse events (such as urinary retention, constipation, sedation, respiratory depression, nausea, vomiting and pruritis)	Number of patients with of urinary retention, constipation, sedation, nausea, respiratory depression, vomiting and pruritis.

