The Biostatistics Unit at the Feinstein Institute for Medical Research [BU-FIMR] will develop a randomization plan for the study using the Biostatistics Randomization Management System [BRMS]. BRMS is a secure, HIPAA-compliant, web-based application that allows investigators to randomize subjects into randomized clinical trials (RCTs) using a personal computer with internet access. A randomization allocation will be generated by the BU-FIMR using the method of permuted blocks. Details of the randomization procedure, including required record keeping will be further developed upon approval of the protocol. The treatment group will receive 2, 2 minute stimulations every 5 hours delivered by a blinded provider. The person assessing the pain intensity, vital signs, and giving pain killers and the participants will be blinded. Pain will be rated pre and post stimulation by the blinded caregiver. During NSCU stay at each stimulation, patients will be on continuous telemetry, and vital signs will be recorded before and at the end of the treatment and hourly for the rest of the day by the blinded caregiver. The control group will receive a sham device, the device is physically identical to the active device, and however no stimulation will be delivered. Patients in either group will be informed that they might feel a tingling sensation or muscle twitch with either device. Before the stimulation is initiated, vital signs will be checked. This includes HR, SBP, MAP, and oxygen saturation. If vital signs are stable, defined as HR>60 beats per minute, SBP> 100 mmHg, MAP> 60 mm HG, and saturation > 90% on room air, nasal cannula or face mask, the stimulation will be provided. In addition, both groups will receive standard of care abortive medications. Pain is usually assessed every 4 hours and as needed, and abortive medications are given depending on the intensity of the headache. 40 patients will be enrolled, and VNS will be performed for up to 10 days.

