Title: Safety and efficacy of non-invasive Vagus Nerve Stimulation (nVNS) in the treatment of headache in Subarachnoid Hemorrhage (SAH)

MAY, 1, 2022

NCT04126408

Overview of study design

This is a single site, randomized, sham-controlled, double-blind study assessing the feasibility, safety, tolerability, and efficacy of non-invasive VNS (nVNS) in the treatment of headache in subarachnoid hemorrhage (SAH).

We hypothesize that two two-minute noninvasive stimulations of the cervical branch of the Vagus nerve, every 5 hours, is efficacious in safely reducing headache intensity and frequency in patients with headache due to SAH, during the patient's intensive care unit (ICU) stay.

After screening and obtaining informed consent, eligible patients diagnosed with SAH on head scans, admitted to the Neurosurgical Intensive Care Unit (NSCU) at Northshore University Hospital will be randomized to either the treatment (stimulation of the cervical branch of the Vagus nerve) or sham (inactive stimulation) group.

Pain intensity will be evaluated every 4 hours. Non-invasive stimulation will be performed every 5 hours.

The treatment arms are the following:

Group 1: Control (patients will receive treatment using an inactive VNS device)

Group 2: Treatment (patients will receive treatment using an active VNS device)

The patients are randomized with equal probability to one of the treatment arms. In total, approximately 40 patients will be recruited

Primary objective

The primary objective of this study is to evaluate the effectiveness of VNS compared to sham device as measured by the mean daily morphine equivalence dosage during the study

Secondary Objectives

The secondary objectives of the study are to compare VNS to sham treatment with respect to effects on the following:

- total overall morphine equivalence dosage
- mean daily headache intensity during the study
- cytokines levels
- blood brain permeability markers in the blood and/or CSF before and after stimulation
- blood brain barrier integrity

Exploratory objectives:

- stroke, vasospasm, DCI, seizure, and central fever
 - The presence of DCI,
 - Transcranial doppler velocity,
 - The number of days with central fever,
 - Incidence of seizures
- severity of cerebral vasospasm during DSA

Safety objectives:

- Opiate related adverse events (such as urinary retention, constipation, sedation, nausea, vomiting and pruritis)
- Occurrence of Adverse Events (AEs)/Serious Adverse Events (SAEs)
- Vital Signs

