- Rate of side effects:
 - o presence of intolerable pain at the stimulation site,
 - o skin irritation,
 - o nasopharyngitis,
 - o hoarseness,
 - o dysgeusia,
 - o shortness of breath,

Outcome measures

Primary efficacy variable:

The daily morphine equivalency dosage by visit

Secondary efficacy variables:

- total overall morphine equivalence dosage
- mean daily headache intensity during by visit
- cytokines levels
- blood brain permeability markers in the blood and/or CSF before and after stimulation
- blood brain barrier integrity

Exploratory variables:

(Stroke, vasospasm, DCI, seizure, and central fever)

- The presence of DCI,
- Transcranial doppler velocity,
- The number of days with central fever,
- Incidence of seizures)
- severity of cerebral vasospasm during DSA

Safety variables:

Opiate related adverse events

- urinary retention,
- constipation,
- sedation,
- nausea,
- vomiting and
- pruritis
- Occurrence of Adverse Events (AEs)/Serious Adverse Events (SAEs)

Rate of side effects: presence of intolerable pain at the stimulation site,

- skin irritation,
- nasopharyngitis,
- hoarseness,
- dysgeusia,

- shortness of breath,
- Vital Signs (weight, BMI, SBP, DBP, and pulse rate are collected at each day)

Statistical considerations

Sample size determination

There are no statistical hypotheses in this study, and therefore there is no sample size justification for this study. This is a feasibility pilot study that will allow us to better calculate the sample size for a large, randomized control study comparing VNS to sham device.

General approach:

- Baseline is defined as the value measured at visit 1 (Day 1). Endpoint is defined as last observed value during visit 14 (Day 14).
- Missing efficacy. Two statistical approaches to handling missing data will be performed in this study.
 - The primary analysis will be a repeated measures analysis of the primary efficacy endpoint. Estimates have been shown to be unbiased when the missing data are missing completely at random and when there is ignorable nonrandom missing data.
 - A secondary analysis will utilize an LOCF analysis
- All statistical tests for treatment difference will be 2-sided and conducted at the 0.05 level of significance.

Analysis populations

The following analysis sets will be used for the statistical analysis and presentation of data:

- ITT: All randomized participants will be included in the Intent To Treat (ITT) population.

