The primary efficacy variable, the daily morphine equivalency dose by visit, will be analyzed using a restricted maximum likelihood (REML)-based repeated measures approach (Mixed Model Repeated Measures (MMRM)). The model for analysis will include fixed, categorical effects of treatment, visit, and treatment by visit interaction, as well as the continuous, fixed covariates of baseline value. An unstructured (co)variance structure will be used to model the within-patient errors. If this analysis fails to converge, compound symmetry will be tested. The (co)variance structure converging to the best fit, as determined by Akaike's information criterion will be used as the primary analysis. The Kenward-Roger approximation will be used to estimate denominator degrees of freedom. The primary treatment comparison will be the contrast between treatments at Day 14 for active treatment versus sham treatment. Treatment group differences contrasts will be computed overall and for each analysis visit (i.e., Day 1, Day 2, Day 3, ..., Day 14) and displayed with the respective 95% CIs. Significance tests will be based on least-squares means and Type III sum-of-squares, using two-sided tests at the 0.05 level (two-sided 95% confidence intervals). No imputed values will be used for the MMRM analysis.

Sensitivity analysis

All analyses on the primary efficacy endpoint will be repeated on the PPS

Additionally, the missing data for the mean daily morphine equivalency dose will be computed using an LOCF algorithm and analyzed using the MMREM model.

Analysis of Secondary and Exploratory Variables

For each of the variables mentioned above, the randomization group difference will be examined using a T-test for continuous variables, and Fisher's exact test for categorical variables at each visit.

Analysis of safety variables

Treatment group differences in the occurrence of serious adverse events will be evaluated using Fisher's exact test.

Adverse events:

The primary safety endpoint of this study is the overall incidence of device related serious AEs. AEs and SAEs will be summarized and presented as proportions and respective 95% exact binomial confidence intervals (CIs).

Frequency and percentage of subjects experiencing a specific adverse event will be tabulated by system organ class, preferred term, and treatment group.

Summary tables and subject data listings will be provided.

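### The stated hypothesis is about headache intensity and frequency, but the primary variable is opioid dose. The SAP plans no overall headache estimate beside it, and frequency and peak dose have no definition or analysis.

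*SAP*

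**What the plan says.** **Hypothesis.** The SAP, Overview of study design, hypothesises that the stimulation "is efficacious in safely reducing headache intensity and frequency in patients with headache due to SAH" during the ICU stay. Protocol 1.1 states the same hypothesis.

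**Primary.** The SAP's primary objective is to "evaluate the effectiveness of VNS compared to sham device as measured by the mean daily morphine equivalence dosage during the study". Its primary efficacy variable is "The daily morphine equivalency dosage by visit". Protocol section 3 names "The difference between the active and sham treatment groups in mean daily morphine equivalence dosage during study", and sections 9.1 and 9.4.2 agree.

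**Headache intensity.** It is secondary in both documents. The SAP, under Analysis of Secondary and Exploratory Variables, compares it by t-test at each visit. Protocol 9.4.3 instead gives it a mixed model of the same form as the dose model.

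**Peak dose.** The synopsis says "mean headache intensity, and mean and peak morphine equivalence dosage during the study period will be compared between the VNS group and the sham group". Peak dose is not mentioned again.

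**Link between dose and pain.** Protocol 4.1 says "abortive medications are given depending on the intensity of the headache". Neither document says how the two results will be read together.

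**The concern.** The sentence that states what the trial is meant to show and the variable that decides the primary analysis are different quantities. They are also coupled: staff see the headache score and respond with analgesic. If they titrate closely, a working device shows mainly as lower dose with similar pain. If they titrate loosely, it shows mainly as lower pain with similar dose. A dose difference can be read as headache relief only when the pain difference is known for the same patients and days.

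Under the SAP as written, the reader would get one modelled dose result with a CI and a series of up to 14 daily t-tests on pain, with no summary to set beside it. Half of the hypothesis, frequency, would go unreported unless someone defined it after seeing the data. The pilot is meant to inform a larger trial (Protocol 9.1 and 9.2), so the meaning of its main outcome should be settled beforehand.

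**Working it through.** **1. Nothing to reproduce.** Neither document gives an effect size, SD or power, and both say the sample size is not justified. The check is a trace through the text.

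| Quantity | In the hypothesis or synopsis narrative? | Endpoint? | Planned analysis |
|---|---|---|---|
| Mean daily opioid dose | Narrative only | Primary, both documents | SAP: MMRM, with overall and per-day contrasts and 95% CIs. Protocol 9.4.2: mixed model |
| Headache intensity | Hypothesis | Secondary, both documents | SAP: t-test per visit. Protocol 9.4.3: mixed model |
| Headache frequency | Hypothesis | None | None |
| Peak opioid dose | Narrative only | None | None |

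The SAP's primary contrast is on dose: "The primary treatment comparison will be the contrast between treatments at Day 14 for active treatment versus sham treatment". It also plans an overall dose contrast, but no counterpart for pain.

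**2. Can frequency be derived?** Pain is rated every 4 hours (Protocol 4.1, 8.1, 10.1.7), so 24/4 = 6 scheduled ratings a day and up to 60 over 10 days. The raw data exist; the definition does not.

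**3. How informative would a pain interval be?** Assume 20 per arm (40 patients, 1:1) and one summary value per patient. The half-width is t(0.975, 38) × √(2/20) = 2.024 × 0.316 = 0.64 SD. If the mITT restriction left 15 per arm (an assumption), it is 2.048 × √(2/15) = 0.75 SD. The difference detectable with 80% power at 20 per arm is (1.960 + 0.842) × √(2/20) = 0.89 SD.

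**4. How often would dose and pain split?** The inputs are assumed: 20 per arm, two-sided 0.05, and a true benefit of 0.8 SD on both outcomes.

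| Dose–pain correlation | Exactly one significant | Dose significantly lower, pain numerically worse |
|---|---|---|
| 0 | 43% | 0.4% |
| 0.3 | 35% | 0.2% |
| 0.6 | 26% | 0.0% |

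The first figure is what power alone predicts. Each test has simulated power of about 0.695, so under independence 2 × 0.695 × 0.305 = 0.42. Splits are common and contradictions are rare when both effects are real.

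**5. A titration model, as a test of a stronger claim.** The inputs are again assumed. Opioid-free headache has mean 7 and SD 2, and the device lowers it by 2 points. Dose = share × (headache − 3) + noise, and observed pain = headache − dose + noise, with noise SD 1.

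| Share titrated | Power on dose / on pain | Dose lower and pain significantly worse |
|---|---|---|
| 25% | 0.28 / 0.61 | 0.0% |
| 50% | 0.59 / 0.43 | 0.0% |
| 75% | 0.73 / 0.17 | 0.2% |
| 90% | 0.77 / 0.06 | 0.6% |

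One test is significant and the other is not in 51% to 75% of these trials. The useful result is qualitative: where the effect appears depends on titration, which the documents do not quantify.

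**The case against.** The strongest reply is that dose is consistently the one primary variable, that both documents disclaim statistical hypotheses, and that the hypothesis sentence is rationale with no decision attached. Protocol 2.3.2 gives a reason for choosing dose: relief of headache should reduce opioid use. Pain is also analysed, and Protocol 9.4.3 models it much as dose is modelled. All of that stands. It makes opioid dose a defensible primary. It does not make the hypothesis sentence agree with it, and it does not supply an overall pain estimate in the SAP, which still plans two-sided 0.05 tests.

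A reader might infer more, and the documents do not support it:

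- **That the same data could both confirm and refute the trial's question.** Dose formally decides, and a non-significant secondary refutes nothing. The 51% to 75% rate of split significance rests on assumed inputs and mostly reflects low power. Lower dose with significantly worse pain occurs in under 1% of trials with a working device.
- **That withheld analgesia would be reported as effectiveness.** With no device effect, dose held back by 1 unit in the active arm only, and a 75% titration share, the dose test favours active in about 40% of trials. That presumes selective withholding. Protocol 4.1 and 6.3 blind participants and the person giving analgesics, and 6.5.1 applies standard-of-care rescue to both groups. The documents offer no mechanism for it.
- **That frequency is never measured and can never be tested.** The 4-hourly ratings could yield it; only a definition is missing.

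**Conclusion.** The point holds as a mismatch of specification. The hypothesis names headache intensity and frequency while opioid dose decides. Intensity has no overall estimate in the SAP, and frequency and peak dose have neither definition nor analysis. This rests on the text and on the stated dependence of analgesia on headache intensity, and on no assumed number. The simulations show only that split results are likely at this size; their effect sizes, correlations and titration shares are assumptions and should not be quoted as the trial's risk of contradiction. The choice of primary need not change. For a pilot this is a modest correction, worth making because the planned reading of the main result is currently incomplete.

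**What to change.** 1. **Hypothesis (Protocol 1.1 and SAP, Overview of study design).** Restate as: *nVNS lowers mean daily morphine-equivalent dose (primary), with headache intensity as the key supporting outcome.*
2. **Frequency and peak.** Either delete frequency or define it from the existing ratings as a descriptive secondary, for example each patient's share of 4-hourly ratings at or above 7, the numeric threshold in the inclusion criteria. Delete peak dose from the synopsis or list it as exploratory.
3. **SAP, Efficacy Analysis.** Analyse headache intensity with the same repeated-measures model, patients and days as dose, with baseline intensity as covariate. Report the overall between-arm difference and 95% CI next to the overall dose difference, and state that a lower dose will be interpreted in light of that interval. Name the days explicitly. Protocol 9.3 removes both outcomes on procedure days when patients are intubated and unconscious; the SAP is silent on this.

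Do not add a rule that allows a claim of benefit only when the pain point estimate does not favour sham. With close titration, pain is nearly level between arms and its sign is close to chance. In the titration model above, with a real effect, such a rule would deny benefit in 11 of every 73 significant dose results (15%) at a 75% share, and 27 of 77 (35%) at 90%. A combined dose-and-pain rank score is optional and not needed to close the gap.

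**Cost.** Wording in two documents and one extra model on data already recorded, with no new visits or patients. The claim becomes more qualified if the pain interval includes worsening. At about 0.64 SD either side, it will do so unless the observed pain benefit is larger than that.

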- Modified ITT (mITT): A modified Intent-to-treat (mITT) population inclusive of all ITT subjects who are treated at least 7 days with at least 3 stimulations of the study device.
- The Per Protocol Set (PPS): Patients who are compliant with the treatment regimen for the duration of the study will be analyzed.
- The safety set will consist of all randomized patients who received at least one stimulation.

The mITT is considered as the primary analysis dataset and will be used for all primary and secondary efficacy analyses. The primary efficacy analyses will be repeated using the PP set. Any discrepancy between the results from the mITT and the PP will be analyzed and discussed.

The secondary variables will be analyzed based on mITT only.

Baseline data and safety analysis will be based on the safety set.

Patient characteristics

In general, data will be summarized by means of summary statistics. Continuous data will be presented with the number of observations, mean value, standard deviation, minimum, median and maximum value. The mean, standard deviation and median will be given with one decimal more than the original values. When applicable, values at each visit, as well as changes from baseline, will be summarized.

Categorical data will be presented as counts and percentages. The data will be presented for each treatment group by visit.

Patient demographics and vital signs will be summarized for all randomized patients. For each of the variables, the treatment group difference will be examined using T-test for continuous variables, and Fisher's exact test for categorical variables.

Efficacy Analysis

The primary analysis of the primary efficacy variable will be based on the mITT population set.

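### The SAP uses the Day 1 dose as both baseline covariate and modelled response, so the first-choice unstructured MMRM has no maximum and the Day 1 and overall contrasts are distorted

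*SAP*

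**What the plan says.** The SAP, under General approach, fixes the baseline: "Baseline is defined as the value measured at visit 1 (Day 1"). Under Efficacy Analysis, the primary variable (daily morphine-equivalent dose by visit) goes into a REML-based MMRM with treatment, visit and their interaction, "as well as the continuous, fixed covariates of baseline value". Treatment contrasts are to be "computed overall and for each analysis visit (i.e., Day 1, Day 2, Day 3, ..., Day 14"), so Day 1 is named as a response visit. The primary comparison is the Day 14 contrast.

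On covariance: "An unstructured (co)variance structure will be used to model the within-patient errors". Then: "If this analysis fails to converge, compound symmetry will be tested". Akaike's criterion chooses among the structures that converge.

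The same model is used again under Sensitivity analysis: "All analyses on the primary efficacy endpoint will be repeated on the PPS", and missing daily doses are to be "computed using an LOCF algorithm and analyzed using the MMREM model".

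Protocol Section 3 says the dose is calculated per day. Protocol 9.4.2 (Version 6, January 2023, later than the May 2022 SAP) describes a simpler mixed model with treatment, time and a random subject effect, and no baseline covariate.

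**The concern.** If the Day 1 dose is both the covariate and the Day 1 response, the model explains that response exactly. An unstructured covariance gives Day 1 its own variance, and that variance can then go to zero. The primary model would fail by construction, whatever the data.

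Three things are at stake. First, the plan would reach its fallback through a specification slip. Second, the SAP would display a Day 1 treatment contrast with a confidence interval that may not describe a treatment effect at all. Third, the overall contrast would average that Day 1 quantity in. The overall contrast is the closest match to the stated objective of mean daily dose during the study. The SAP also says the pilot is meant to help size a larger trial, so the size of the estimate matters as well as its p-value.

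**Working it through.** **Inputs.** From the SAP: about 40 patients, 1:1; Days 1 to 14 as responses; one common baseline slope; unstructured, then compound symmetry. The protocol's intervention lasts up to 10 days, so 10 visits were also examined. The documents give no SD, correlation, effect size or dropout. The assumed values are a mean of 17 mg, SD 10 mg, and the correlations and effects stated below. The no-maximum result depends on none of them.

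**1. No maximum.** For arm g the Day 1 residual is y1 − mu1g − b·y1. At b = 1 and mu1g = 0 in both arms it is zero for every patient. Let the Day 1 variance be s. The determinant term contributes n·ln(s) to −2 log REML. The REML correction contributes −3·ln(s), for the two Day 1 means and the slope, and the Day 1 quadratic term is zero. So −2 log REML changes as (n − 3)·ln(s) and falls without limit as s goes to 0, for any n above 3. The log-likelihood gain per tenfold fall in s is (n − 3)/2 × ln(10):
- n = 40: 18.5 × 2.3026 = 42.598 (same for 14 or 10 visits)
- n = 30: 13.5 × 2.3026 = 31.085

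Numerical check (n = 40, complete data, correlation 0.5): along a path with s = 1, 1e-2, 1e-4, 1e-6 and 1e-8, −2 log REML was 3536.5, 3366.2, 3195.8, 3025.4 and 2855.0. The later steps are 170.4 per two decades, i.e. 85.2 = 37 × ln(10) per decade. An EM fit reached s = 3e-11 with slope 0.9999993 and was still improving. A general optimiser (not a mixed-model package) converged in 0 of 9 simulated data sets with Day 1 as a response and in 9 of 9 with Days 2 onward.

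**2. After removing Day 1 from the responses.** On the same data, the unstructured fit settled at −2 log REML = 3331.46, slope 0.657, with 13 × 14/2 = 91 covariance parameters in place of 14 × 15/2 = 105.

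**3. Day 1 contrast under compound symmetry.** It equals (1 − slope) × the raw Day 1 difference, to rounding. Over 150 simulated trials per correlation, with no Day 1 effect:

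| Correlation | Reported SE (mg) | Actual SD (mg) |
|---|---|---|
| 0.3 | 2.97 | 1.98 |
| 0.5 | 2.68 | 1.50 |
| 0.7 | 2.20 | 0.92 |

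**4. Overall contrast under compound symmetry.** If the effect is constant from Day 2 and zero on Day 1, the contrast is (T − 1)/T of that effect: 13/14 = 0.929 or 9/10 = 0.900. With a true −4 mg at correlation 0.3, the mean estimate was −3.82 with Day 1 and −4.12 without. The SE shrinks equally (1.524 against 1.641), so the ratio of mean estimate to mean SE is −2.51 both ways.

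**5. Day 14 contrast under compound symmetry, Day 1 before stimulation.** The mean estimate hardly moves (−3.999 with Day 1, −4.005 without, correlation 0.3). The reported SE falls by 1.9%, 2.5% and 3.1% at correlations 0.3, 0.5 and 0.7 (for example 2.682/2.752 = 0.975). Across several assumed true covariances, keeping Day 1 added 0.5 to 1.8 percentage points to last-day type I error with complete data. The SAP's mITT rule requires patients to be "treated at least 7 days with at least 3 stimulations of the study device", so dropout was also tried, with an assumed last day uniform from Day 7. The addition was then 0.1 to 0.4 points (14 visits) or 0.3 to 1.4 points (10 visits), with simulation SE 0.2 to 0.4. The dropout runs used Satterthwaite degrees of freedom, not the SAP's Kenward-Roger.

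**6. If software accepted the singular fit, Day 1 before stimulation.** The slope is forced to 1 and Day 14 becomes the difference in change from Day 1: −1.240 − 2.405 = −3.645 in the worked data set. Relative to proper baseline adjustment, with equal variances, the variance ratio is 2(1 − rho)/(1 − rho²) = 2/(1 + rho): 1.54, 1.33 and 1.18 at correlations 0.3, 0.5 and 0.7. No run behaved this way.

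**7. If Day 1 includes stimulation.** An effect d present from Day 1 onward leaves (1 − slope) × d in the adjusted contrasts: about half at slope 0.5, none at slope 1. Taking Day 1 out of the responses does not cure this.

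**The case against.** The strongest reply is that little harm reaches the primary result. The SAP already has a fallback, which can be fitted. Its covariance is what the protocol's random subject effect implies. If Day 1 precedes stimulation, the Day 14 estimate is nearly unchanged under it. Even the singular limit would give a valid, though less efficient, change-score contrast with complete data. The overall test statistic is unaffected, and the Day 1 standard error is too large, so it would not generate false findings. The protocol's timetables show intervention from Day 2, which leans towards a pre-stimulation Day 1. The trial is a pilot with no formal hypothesis.

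Much of this stands. The 14-visit dropout increment in type I error is within simulation noise. Removing Day 1 also does not guarantee an unstructured fit. With k response visits and earlier visits complete, the last visit needs at least k + 3 patients: 16 with a Day 14 value if k = 13, or 12 with a Day 10 value if k = 9. How Day 14 fits an intervention of up to 10 days is a separate matter to reconcile.

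It does not remove the defect. Nothing in the SAP takes Day 1 out of the responses, and the later protocol model does not correct the SAP's more detailed one. The fallback repairs neither the Day 1 contrast nor the size of the overall estimate. If software did report convergence near the singular point, the Akaike rule would favour that fit because its likelihood keeps rising. The timing is not settled either: the protocol's schedule labels Days 2-5 as enrolment and baseline, its flow figure puts baseline assessments and intervention together on Days 2-4, and neither is mapped to SAP Day 1. The SAP does plan tests at the 0.05 level.

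**Conclusion.** The concern holds. As written, the covariance structure named first for the primary analysis has no REML maximum for any realistic number of patients. This rests only on the SAP text and on the dose being one value per day.

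The practical size depends on timing:
- **Day 1 before stimulation, fallback used.** Harm to Day 14 is small. The Day 1 contrast has no meaning as a treatment effect, and a constant effect from Day 2 is understated in the overall contrast by 7.1% (14 visits) or 10% (10 visits).
- **Day 1 includes stimulation.** The covariate carries device effect, and every adjusted contrast, including Day 14, is biased towards zero by an amount set by the slope.

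The type I error and precision figures rest on assumed correlations and dropout. This should be corrected before analysis; it does not undermine the trial.

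**What to change.** In the SAP:
- Use the baseline dose as a covariate only. Start the modelled responses and every contrast, including the overall one, on the day after the baseline day (Day 2 if Day 1 is baseline), and delete the Day 1 contrast.
- Apply the same to the per-protocol and LOCF re-runs.
- State how SAP Day 1 maps to the protocol's day labels and whether it precedes the first stimulation. If it does not, take the baseline dose from a window that ends before the first stimulation.

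If Day 1 does precede stimulation, a valid alternative is to keep it as a response, drop the covariate and constrain the two arms to a common Day 1 mean. The overall contrast should still begin on the following day.

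The cost is a few lines of text. Protocol 8.1 says opiate use is already in the electronic medical record, so a pre-stimulation window needs no new data collection.
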